	
on Days 3, 7, 14, 28, 42, 56, 70, and 112. Pharmacodynamics sampling (serum immunoglobulin levels) will occur at Baseline, Day 3 and weekly thereafter through the Week 8 visit, then once every two weeks through Week 16 (i.e., Weeks 10, 12, 14, and 16).
 
Sentinel subjects will be utilized; the first two subjects in each cohort will be randomized to receive either VIS649 (n=1) or placebo (n=1) and will receive study drug at least 24 hours before the remaining subjects in the cohort (7 subjects) are dosed. These 2 subjects shall remain confined to the study center for 24 hours after study drug administration.
 
The safety profile of these subjects over the 24 hour post-administration period will be reviewed to determine whether it is appropriate to proceed with enrollment of the remaining subjects in the cohort as planned. This will occur for each dose escalation. The remaining 7 subjects in each cohort will be randomized to receive VIS649 (n=6) or matched placebo (n=1).
 
The maximum duration of participation (Screening through End-of-study) for individual subjects will be approximately 20 weeks (5 months) with the possibility to extend up to 28 weeks (7 months). Each subject will participate in screening period lasting 1 to 28 days (0 to 4 weeks), an in-house stay for 2 to 3 days, and a post-administration period of 16 weeks. The scheduled final visit will occur 16 weeks post-dosing (112 days); however, two additional follow-up visits may be performed, at Weeks 20 and 24 post-dosing, if serum immunoglobulins have not returned to >lower limits of normal by the Week 16 visit or if emerging trial data suggest a value of later follow-up (i.e., for detection of anti-drug antibody responses).

Investigational Product	Medicinal
Number of Subjects	Up to 45 subjects may be enrolled. A total of 20 Japanese subjects (4 subjects per cohort) and 25 non-Japanese subjects (5 subjects per cohort) may be enrolled and randomized to receive a single dose of VIS649 or placebo. No more than one Japanese subject per cohort, may be randomized to receive placebo. Safety, PK and PD data from the initial four dosing cohorts will be assessed, to determine whether to initiate a fifth dosing cohort at a dose not to exceed 20 mg/kg.
Study Population	Healthy, non-smoking male and female subjects, 18 to 55 years of age with a body mass index between 18 and 32 kg/m ² , are planned for enrollment.

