3. OVERALL DESIGN AND PLAN OF THE STUDY

3.1. Overview

This is a phase 1, randomized, placebo-controlled, double-blind, single ascending dose study to investigate the safety, tolerability, PK/PD of the IV administration of VIS649 in healthy subjects.

The study will be conducted in four sequential dosing cohorts enrolling nine subjects per cohort, with an optional fifth cohort. Each cohort will have 4 Japanese subjects. Subjects will be randomized to VIS649 or placebo in a ratio of 7:2 (7 active, 2 placebo). No more than one Japanese subject per cohort may be randomized to receive placebo. Safety, PK and PD data from the initial cohorts will be assessed, to determine whether to initiate a fifth dosing cohort at a dose not to exceed 20 mg/kg.

The study comprises of:

- A Screening Visit up to 28 days before dosing
- An in-house stay for approximately 2-3 days, with admission to the study center on Day -1, dosing on Day 1, and discharge in the morning of Day 2
- A post-administration period of 16 weeks
- Outpatient visits, on Day 3 (+1 day), 7 (\pm 1 day), 14, 21, 28, 35, 42, 49, 56, 70, 84 and 98 (all visits \pm 3 days)
- A final Follow-up visit on Day 112 (\pm 3 days); Two additional follow-up visits may occur, at Weeks 20 and 24 post-dosing, if serum immunoglobulins have not returned to $>$ lower limits of normal by the Week 16 (Day 112) visit, or if emerging trial data suggest a value of later follow-up (i.e., for detection of ADA responses).

The total duration of the clinical study per subject will be up to approximately 20 weeks (5 months), including the Screening period with the possibility of duration extending to 28 weeks (7 months) if follow-ups visits are required.

Potential subjects will be carefully screened for eligibility prior to study enrollment. Randomization and blinding will occur according to a core randomization list administered by the site's unblinded pharmacist.

Eligible subjects will report to the Clinical Pharmacology Unit (CPU) at study check-in (Day -1) and will be required to stay in the CPU until Day 2 (24 hours post infusion). On Day 1, a single

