5.2. Rationale for Starting Dose and Dose Escalation

VIS649 will be administered at a first-in-human starting dose of 0.5 mg/kg IV to healthy volunteers. The starting dose was selected upon consideration of the VIS649 target and mechanism of action, *in vitro/in vivo* toxicology data, the NOAEL observed in the pivotal toxicology study in cynomolgus monkeys, and estimations derived from a PK/PD model of the pharmacologically active dose in humans. In each dosing cohort, two subjects (one receiving placebo, the other receiving VIS649) will be dosed 24 hours before others in the respective cohort, to provide a sentinel function should unanticipated adverse reactions occur at any dose level.

The cynomolgus monkey is considered a relevant species for evaluation of VIS649 toxicity due to similarity in B cell biology, 99% sequence homology between cynomolgus and human APRIL, and similar binding affinity of VIS649 to cynomolgus and human APRIL (within ~2-fold). The effects of multiple doses of VIS649 were evaluated in a GLP toxicology study in healthy cynomolgus monkeys at 25, 50, and 100 mg/kg IV once weekly over 28 days. VIS649 was well tolerated in cynomolgus monkeys with no VIS649-related clinical findings up to 100 mg/kg; the NOAEL from this study was 100 mg/kg.

A maximum recommended starting dose of 5 mg/kg was identified by considering the NOAEL of 100 mg/kg in cynomolgus monkeys, which translates to a human equivalent dose of 100 mg/kg for monoclonal antibody therapeutics. Applying a safety factor of 2X that accounts for the measured affinity difference of VIS649 for monkey and human APRIL, and an additional 10X

safety factor to account for potential interspecies differences and other unknowns arrives at a NOAEL justified starting dose of 5 mg/kg, which is expected to be well tolerated in humans based on cynomolgus monkey studies.

[REDACTED]

The minimum pharmacologically active dose of 0.5 mg/kg was selected as the starting dose for evaluation in healthy volunteers; this is 10-fold lower than the maximum recommended starting dose based on the NOAEL. Doses from 0.5 to 12 mg/kg will be evaluated in single dose escalation in four cohorts, while a final cohort to receive a dose greater than 12 mg/kg but no greater than 20 mg/kg may be enrolled, based on emerging clinical, PK and/or PD data. Dose escalations will not exceed a 4-fold increase. The safety margins for targeted clinical doses are provided in [Table 4](#).

[REDACTED]

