5.5.2. Randomization numbers

Prior to dosing on Day 1, eligible subjects will be assigned a randomization number in accordance with the randomization code generated by PAREXEL International. The randomization code will be maintained in a room with restricted access to pharmacy personnel only. The randomization code will include 4-digit subject numbers [REDACTED] Cohort and randomization numbers list in [Table 5](#).

Table 5 Randomization Numbers and Treatment Assignment

Dose Group	Randomization Numbers	Replacement Numbers	Treatment Assignment	
Cohort 1	[REDACTED]	[REDACTED]	0.5 mg/kg VIS649 (N=7)	Placebo (N=2)
Cohort 2	[REDACTED]	[REDACTED]	2.0 mg/kg VIS649 (N=7)	Placebo (N=2)
Cohort 3	[REDACTED]	[REDACTED]	6.0 mg/kg VIS649 (N=7)	Placebo (N=2)
Cohort 4	[REDACTED]	[REDACTED]	12 mg/kg VIS649 (N=7)	Placebo (N=2)
Optional Cohort 5	[REDACTED]	[REDACTED]	Up to but not greater than 20 mg/kg VIS649 (N=7)	Placebo (N=2)

Once a randomization number has been allocated to one subject, it may not be assigned to another subject. If subjects withdrawn prematurely from the study and are replaced under the direction of the Sponsor, then a replacement randomization number will be assigned. A replacement randomization code will be generated such that replacement subjects are assigned to the same treatment as the discontinued subjects. The replacement randomization code will differ only in randomization numbers, which will be 4-digit numbers [REDACTED]
[REDACTED]
[REDACTED]

No more than one Japanese subject per cohort may be randomized to receive placebo.

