5.8. Blinding and Breaking the Blind

The clinical study will be performed in a double-blind manner, for clinical research unit staff interacting with study participants, with the exception of the persons involved in the preparation of the IMPs. These persons will not be involved in any other study activities.

Prior to scheduled unblinding as described below, the study blind should not be broken except in a medical emergency (where knowledge of the study drug administered would affect the treatment of the emergency). The decision to break the blind will be made on a case-by-case basis, at the discretion of the Principal Investigator in collaboration with the Sponsor/Medical Monitor. The applicable Standard operating procedure (SOP) will be followed for blind breaking procedures.

As participants in each dosing cohort complete their Week 16 visit, data clean-up and soft-lock will be performed for each cohort, to allow interim assessments of blinded data. PK/PD analysts will have access to unblinded data at all times, but those individuals will not be involved in study participant interactions. Summaries of treatment specific PD responses (principally, individual immunoglobulin levels over time and group mean, median, minimum and maximum parameters by treatment assignments) will be prepared and shared with the Sponsor, in a manner that does not unblind individual patient treatment assignments. A registry of dummy subject identifiers will be created. A physician who is not involved in the study will review Ig results to maintain the blind for the Principal Investigator.

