3.4 Randomization

Randomization and blinding will occur according to a core randomization list administered by the site's unblinded pharmacist.

PAREXEL International
Statistical Analysis Plan

Prior to dosing on Day 1, all screened and eligible subjects will be assigned a randomization number in accordance with the randomization code generated by PAREXEL International. If subjects are withdrawn prematurely from the study and are replaced under the direction of the Sponsor, then a replacement randomization number will be assigned. Cohort, randomization numbers and replacement numbers are listed in Table 3.

Table 3 Randomization Numbers and Treatment Assignment

Dose Group	Randomization Numbers	Replacement Numbers	Treatment Assignment	
Cohort 1	[REDACTED]	[REDACTED]	0.5 mg/kg VIS649 (N=7)	Placebo (N=2)
Cohort 2	[REDACTED]	[REDACTED]	2.0 mg/kg VIS649 (N=7)	Placebo (N=2)
Cohort 3	[REDACTED]	[REDACTED]	6.0 mg/kg VIS649 (N=7)	Placebo (N=2)
Cohort 4	[REDACTED]	[REDACTED]	12 mg/kg VIS649 (N=7)	Placebo (N=2)
Cohort 5	[REDACTED]	[REDACTED]	VIS649 6.0 mg/kg plus vaccine (N=10)	Placebo plus vaccine (N=5)

No more than one Japanese subject per cohort may be randomized to receive placebo in cohorts 1-4. No more than two Japanese subjects may be randomized to receive placebo in cohort 5.

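### With a cap of one Japanese placebo subject per cohort and no readable limit on sentinel ethnicity, a pair of Japanese sentinels reveals that the cohort's other two Japanese subjects are on VIS649

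*Protocol*

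**What the plan says.** Three rules meet here.

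- **Ethnic make-up.** Protocol Section 3.1: "Each cohort will have 4 Japanese subjects". With nine per cohort, that leaves five non-Japanese.
- **Sentinels.** Protocol Section 5.2: "two subjects (one receiving placebo, the other receiving VIS649) will be dosed 24 hours before others in the respective cohort". The synopsis (Study Design) gives the same 1:1 pair and splits the other seven subjects six active to one placebo. SAP Section 3.1 keeps the pair for cohorts 1-4 and drops it for cohort 5.
- **Cap.** Protocol Section 5.5.2: "No more than one Japanese subject per cohort may be randomized to receive placebo". SAP Section 3.4: "No more than one Japanese subject per cohort may be randomized to receive placebo in cohorts 1-4".

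No readable sentence limits the ethnicity of the sentinels, sets a minimum number of Japanese placebo subjects, or describes stratification by ethnicity. The randomization number ranges in both documents and part of Protocol Section 5.5.2 are redacted.

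On the blind, Protocol Section 5.8 says: "The clinical study will be performed in a double-blind manner". This covers unit staff who interact with participants. The same section has an uninvolved physician review the immunoglobulin results so that the Principal Investigator stays blinded.

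**The concern.** Taken together, the rules can disclose treatment without anyone opening the code. Two Japanese sentinels contain exactly one placebo, which uses up the cap. The other two Japanese subjects in the cohort must then be on VIS649, and this is known before they are dosed. The deduction needs only the protocol text, the dosing order and knowledge of who is Japanese, which is an eligibility item in Protocol Section 4.2.

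The primary endpoint is the proportion of subjects with AEs and SAEs. The Principal Investigator rates severity and causality (Protocol Section 6.2.1.3), and the two AE stopping criteria in Section 3.4 use those ratings. The Investigator also sits on the committee that reviews blinded safety data for escalation (Section 3.1). A rater who knows that a subject is on active drug may judge causality differently.

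Separately, the cap has no floor, so the number of Japanese placebo subjects is not fixed, although the SAP tabulates PD and ADA results by ethnicity and treatment.

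**Working it through.** **Inputs.** Nine subjects per cohort, 4 Japanese (J) and 5 non-Japanese (N) (Protocol 3.1, 4.1). Sentinel pair 1 active : 1 placebo, remaining seven 6 : 1 (synopsis). At most one J on placebo (Protocol 5.5.2, SAP 3.4). Four cohorts carry both rules in the SAP.

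**Check of the plan's own figure.** Active 1 + 6 = 7 and placebo 1 + 1 = 2, which reproduces 7:2 per cohort of nine.

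**Step 1: what can be deduced.** Without the cap there are 2 × 7 = 14 placements of the two placebos, and each remaining subject has P(placebo) = 1/7, so P(active) = 6/7. The cap removes every placement with two J on placebo. The documents do not describe how the list is made, so two mechanisms are shown: (A) uniform over admissible lists; (B) sentinels 50/50, then uniform over what the cap still allows.

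| Sentinels | Remaining | Placements excluded | P(placebo), remaining J | P(placebo), remaining N |
|---|---|---|---|---|
| N, N | 4 J, 3 N | 0 of 14 | 1/7 | 1/7 |
| J, N | 3 J, 4 N | 3 of 14 | 1/11 (A), 1/14 (B) | 2/11 (A), 11/56 (B) |
| J, J | 2 J, 5 N | 4 of 14 | **0** | 1/5 |

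The zero in the last row holds for any list that respects the cap. In that row the sentinels remain at 1/2 each.

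**Step 2: how often.** If the pair is a random two of the nine:

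- P(both J) = 4/9 × 3/8 = 1/6 per cohort
- P(at least one of four cohorts) = 1 − (5/6)^4 = 0.518
- Expected subjects affected = 4 × 1/6 × 2 = 1.33 of 36

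If the pair's make-up and the placements are instead conditioned jointly on the cap, there are 10 N,N pairs, 20 mixed pairs and 6 J,J pairs:

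- Admissible configurations = 10 × 14 + 20 × 11 + 6 × 10 = 420
- P(both J) = 60/420 = 1/7 per cohort
- P(at least one of four) = 1 − (6/7)^4 = 0.460
- Expected subjects affected = 4 × 1/7 × 2 = 1.14 of 36

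**Step 3: Japanese placebo count, cohorts 1-4.** Each cohort contributes 0 or 1, so the permitted range is 0 to 4 among 4 × 2 = 8 pooled placebo subjects. P(one J placebo in a cohort), and the resulting binomial probabilities over four cohorts:

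| Mechanism | P(1) per cohort | P(2 or fewer) | P(0) |
|---|---|---|---|
| Joint conditioning | 1 − 140/420 = 2/3 | 33/81 = 40.7% | 1/81 = 1.2% |
| A, random pair | 5/18 × 4/7 + 5/9 × 7/11 + 1/6 = 0.679 | 38.6% | 1.1% |
| B, random pair | 5/18 × 4/7 + 5/9 × 5/7 + 1/6 = 0.722 | 30.9% | 0.6% |

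(The 140 comes from 10 × 6 + 20 × 4 admissible configurations with no J on placebo.)

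**Step 4: effect of limiting the pair to at most one J.** Only the first two rows of the Step 1 table remain possible. No remaining subject then has P(placebo) of 0 or 1 while the sentinels stay blinded.

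**The case against.** The strongest reply is that the defect is inferred from silence next to redacted text. A cap by ethnicity needs some ethnicity-linked allocation, and the hidden list may already use a mixed pair or a fixed split. This stands as a limit: a reader might infer that the list leaves sentinel ethnicity uncontrolled, or that the blind was in fact broken, and the documents show neither. They show only that the readable rules permit the disclosure.

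Second, the leak is small. Staff already know that each non-sentinel has a 6/7 chance of active drug, and two subjects per affected cohort move from there to certainty. This also stands. A reader might think that the sentinels are revealed too; they are not.

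Third, the effect on escalation is easy to overstate. Protocol Section 3.4 allows relevant subjects to be unblinded when a criterion is met, the pause depends on actual assignment, and most criteria are laboratory, ECG or vital-sign thresholds. The text does not support a claim that escalation decisions are compromised. What remains exposed is the rating of AE severity and causality. The documents also do not say who confirms ethnicity, so it cannot be asserted that blinded staff do so.

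Fourth, the missing floor might be read as undermining the ethnicity objective. It does not. That objective concerns PK only, and the PK population requires a quantifiable VIS649 concentration, so placebo plays no part. The 0 to 4 range comes from the cap alone, not from the sentinel rule, and it touches only descriptive by-ethnicity PD and ADA tables.

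**Conclusion.** The point holds as a narrow blinding gap. Whenever both sentinels are Japanese, two further subjects in that cohort are certainly on VIS649 to anyone who knows the protocol, the dosing order and who is Japanese. That deduction needs no statistical assumption beyond a list that obeys the cap.

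Its frequency does rest on assumptions: 1/6 per cohort and 52% over cohorts 1-4 with a random pair, or 1/7 and 46% with joint conditioning. The expected number affected is at most about 1.3 of 36. The 52% should not be paired with the 41% chance of two or fewer Japanese placebo subjects, because they come from different models.

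The absent floor is secondary. Two or fewer Japanese placebo subjects in cohorts 1-4 has a probability of about 31% to 41%, depending on the mechanism. For comparison, SAP Sections 4.3.7, 4.3.8 and 4.3.10 drop cohort 5 from by-ethnicity analysis when either group has fewer than three subjects. A count of zero is permitted but has a probability of only about 1%.

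This is a cheap improvement that protects investigator-rated AEs, not a flaw that threatens the trial's conclusions.

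**What to change.** In Protocol Sections 3.1 and 5.5.2, state that no more than one subject of each sentinel pair may be Japanese (for example, one Japanese and one non-Japanese), and keep the cap. A matching sentence in the synopsis and Section 5.2, where the pair is described, keeps the text consistent. If the list already controls this, saying so is enough. The cost is a small scheduling constraint on the pair; no subjects are added and 7:2 is unchanged.

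The SAP says that the cohort 5 dose was already evaluated in cohort 3. For cohorts already dosed, SAP Section 3.4 should therefore describe what was done rather than be changed.

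Optional: fixing exactly one Japanese and one non-Japanese placebo per cohort would guarantee 4 and 4 in cohorts 1-4. It works only with a mixed pair, when remaining subjects have P(placebo) = 1/2 × 1/3 = 1/6 (Japanese) and 1/2 × 1/4 = 1/8 (non-Japanese). Without a mixed pair, two non-Japanese sentinels would reveal the other three non-Japanese subjects, and two Japanese sentinels would still reveal two. It also has a blinding cost: unblinding one sentinel would always identify the remaining 3 Japanese or the remaining 4 non-Japanese subjects as active. Under the cap alone, a mixed pair with the non-Japanese sentinel on placebo identifies none of the remaining seven. The sponsor should weigh this against a gain confined to descriptive tables.

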5.6. Administration of Investigational Medicinal Products

The amount of VIS649 will be calculated on a per subject weight basis and administered diluted in 100 mL of 0.9 % sodium chloride. VIS649 will be administered intravenously using a volumetric pump and through a 0.22 μ m in line IV filter at a rate of 100 mL/hr over the course of one hour. A saline flush is performed after the infusion is complete to ensure that any drug product remaining in the infusion line is administered. Placebo will be 100 mL of 0.9% sodium chloride administered IV in an identical manner. Refer to the pharmacy manual for specific details on storage, handling, and preparation information.

5.7. Compliance

Dosing will be performed by trained, qualified personnel designated by the Principal Investigator. The date, time and volume of the administered dose will be documented. Comments will be recorded if there are any deviations from the planned dosing procedures.

5.8. Blinding and Breaking the Blind

The clinical study will be performed in a double-blind manner, for clinical research unit staff interacting with study participants, with the exception of the persons involved in the preparation of the IMPs. These persons will not be involved in any other study activities.

Prior to scheduled unblinding as described below, the study blind should not be broken except in a medical emergency (where knowledge of the study drug administered would affect the treatment of the emergency). The decision to break the blind will be made on a case-by-case basis, at the discretion of the Principal Investigator in collaboration with the Sponsor/Medical Monitor. The applicable Standard operating procedure (SOP) will be followed for blind breaking procedures.

As participants in each dosing cohort complete their Week 16 visit, data clean-up and soft-lock will be performed for each cohort, to allow interim assessments of blinded data. PK/PD analysts will have access to unblinded data at all times, but those individuals will not be involved in study participant interactions. Summaries of treatment specific PD responses (principally, individual immunoglobulin levels over time and group mean, median, minimum and maximum parameters by treatment assignments) will be prepared and shared with the Sponsor, in a manner that does not unblind individual patient treatment assignments. A registry of dummy subject identifiers will be created. A physician who is not involved in the study will review Ig results to maintain the blind for the Principal Investigator.

5.9. Prior and Concomitant Medications

Any medicinal product, prescribed or OTC, including herbal and other nontraditional remedies, is considered a concomitant medication. Prior and concomitant medication use will be recorded for the 30 days prior to the Screening Visit until the End-of-study Visit. Prior and concomitant medication use is not permitted from last 30 days or five half-lives, whichever is longer, preceding Baseline (Day -1) until end-of-study (including prescription or non-prescription [over-the-counter]) medication, except, acetaminophen or ibuprofen, hormonal contraceptives, topical medications, vitamins, dietary or herbal). However, concomitant medication use may be warranted for the treatment of AEs. The use of concomitant medications to treat AEs should be discussed between the Principal Investigator and the Medical Monitor.

